based on data submitted from the ELLIPSE clinical trial, which was published in the New England Journal of Medicine in April 2019⁶³. This trial showed superior efficacy of liraglutide with metformin compared to placebo + metformin for lowering HbA1c. Liraglutide improves overall glucose homeostasis by enhancing glucose-dependent insulin secretion, reducing glucagon secretion and delaying gastric emptying⁶⁴. In addition, liraglutide also lowers fasting glucose concentrations^{64,65} but the exact mechanism of action has not been extensively investigated. It is presumed that liraglutide lowers fasting glucose primarily by increasing the endogenous insulin: glucagon ratio that subsequently inhibits hepatic gluconeogenesis and glycogenolysis⁶⁶. However, GLP-1 agonists may also directly lower hepatic glucose production: an extra-pancreatic effect demonstrated in murine models⁶⁷, as well as in elegant experiments using prolonged GLP-1 infusion during pancreatic clamps in healthy individuals⁶⁸. If liraglutide decreases glucose production specifically by reducing gluconeogenesis, it would also be important for targeting this early pathological feature of type 2 diabetes in youth.

Study Objectives

The primary objective of this study is to compare the change in gluconeogenesis between the two intervention arms (combination therapy of metformin and liraglutide and metformin only) in African-American youth.

Primary outcome: The change in gluconeogenesis from baseline (prior to study drugs) to 12 weeks.

Secondary outcomes: The change from baseline to 12 weeks in:

1. Glucose production
2. GLP-1 and GIP area under the curve concentrations (AUC) during OGTT and meal absorption
3. Insulin sensitivity
 - a. Hepatic insulin sensitivity
 - b. Whole body insulin sensitivity
4. Insulin area under the curve concentrations during an OGTT and meal absorption
5. Glycerol and palmitate turnover as an indicator of lipid metabolism.

Exploratory outcomes:

Pharmacogenomic variants of metformin response:

1. Identify the 9 known variants of metformin response (Table 1) in African-American youth with type 2 diabetes
2. Generate a composite genetic risk score based on these 9 variants and determine the relationship of this composite risk score with:
 - a. Serum and urine metformin concentrations
 - b. Change in gluconeogenesis from baseline to 12 weeks.
3. Screen for unknown genomic variants in metformin response in specific genes of interest.

Gut microbiome and metformin

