Stable isotope administration will begin the night of the admission; glucose appearance, fractional gluconeogenesis and glycerol turnover will be measured with [6,6²H₂]glucose, deuterated water [²H₂O], [¹³C₁₆]potassium palmitate and [²H₅]glycerol respectively. Lean body mass (LBM) measurements from dual x-ray absorptiometry scans will be used to calculate the isotope administration rates. Deuterated water (3 gram•kg_{LBM}) will be administered in 3 divided doses at 9pm, 12am, and 3am. Primed (60×the minute infusion rate) and continuous infusions of [6,6²H₂]glucose and [²H₅]glycerol will start at 4am (t= -240m) and continue until 9am (t= 0m). At 730am, an unprimed [¹³C₁₆] palmitate infusion will be started. At 9am (t= 0m), the glycerol and palmitate infusions will be discontinued. The [6,6²H₂]glucose infusion will continue until 2pm (300m) to quantify gluconeogenesis during meal absorption using a continuous feeding protocol with a nutrient drink and [6,6²H₂]glucose intravenous infusion will be used to mimic the steady-state prandial state^{70,71}. At 9am (t= 0m), participants will be fed a lactose-free nutrient drink to provide ~50% of estimated total energy needs and macronutrient composition that matches the previous days' meals in equal portions every 30 minutes over the 5h

of feeding. The purpose of this feeding strategy is to evaluate the acute response to refeeding, and not to provide full caloric requirements⁷¹. Isotope enrichment will be measured over a period of 30 minutes during steady state. Therefore, blood samples for steady-state conditions will be obtained at the following time periods: (1) fasting between 830-9am (t= -30 to 0m) and (2) prandially between 130-200pm (t=270 to 300m). Blood samples for hormones and metabolites (including glucose, insulin, incretins in protease inhibitor treated tubes) will be collected every 30 minutes between 9am and 2pm. Whole blood will be centrifuged and plasma transferred and frozen at -80C until analyses.

c. Urine collection

A timed 24-hour urine collection to measure urinary nitrogen will start at noon on admission and continue until noon on the study day. Total daily urinary nitrogen excretion will be used to determine the total body glucose and lipid oxidation rates as previously described⁷².

d. Indirect calorimetry

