Participants will return for an inpatient tracer visit protocol after 12 weeks \pm 14 days on study medication. Participants will receive their last dose of study medication at supper in the evening of admission Day 1 during Visit 5.

Visit 5 procedures will be identical to Visit 2 above with the following additional blood sampling for metformin concentrations. To measure blood (plasma and RBC) plasma samples for metformin for participants within the study receiving metformin at doses 1000-2000mg daily. Samples for metformin analysis (3ml of whole blood) will be collected, processed for isolation of plasma and RBC and frozen at -80C until analysis during the OGTT as follows:

- a) Day 1 during the OGTT at time 0, 0.5h, 1h, 1.5h, 2h, 3h 4h, 6h, 8h and 8pm (pre-second dose).
- b) Day 2 at 8am and at 2pm

After completion of Visit 5, participants will be instructed to resume their home medication regimen.

Study Agents/ Intervention

Two study agents will be used: metformin oral 500mg oral tablet and liraglutide (6mg/ml, 3ml) solution for subcutaneous injection, pre-filled, multi-dose pen that delivers doses of 0.6mg, 1.2mg or 1.8mg. Both metformin and liraglutide will be used within the approved dosing regimens. Neither drug will be altered from the approved dosage formulation. Table 3 illustrates the titration schedule for each study drug.

Table 3: Titration Schedule for Metformin and Liraglutide

Study schedule	Week	Liraglutide (subcutaneous injection)	Metformin (oral tablet)
Run-in	-1 to 0	-	-
After baseline visit	0-1	0.6mg once daily	500mg once daily
	1-2	1.2mg once daily	500mg twice daily
Target study dose	3-12	1.8mg once daily	1000mg twice daily

The participant will start the study drug(s) on Day 2 of Visit 2, after the tracer protocol is completed. The PI will review blood glucose logs and/ or CGM readings weekly and ensure that the study drug(s) titrated to the highest tolerable dose as guided by Table 3 above. For patients on combination therapy, the dose of liraglutide will not be increased if the fasting blood glucose is <75 mg/dl on 2 or more consecutive days. If the fasting blood glucose subsequently rises to ≥90 mg/dl on 2 or more consecutive days, the dose of liraglutide will increase by 0.6mg once daily every 5-7 days to achieve maximum tolerable dose.

Dose titration for gastrointestinal intolerance

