Examples include participants with a history of active thyroid disease, liver disease, pancreatitis, nephrotic syndrome or lupus. Liraglutide may be associated with an increased risk for pancreatitis and C-cell carcinoma. Therefore, any individual with a history of acute or chronic pancreatitis, or increased risk for pancreatitis as indicated by elevated serum triglycerides $\geq 500\text{mg/dl}$ at baseline, will be excluded. Hypertriglyceridemia is a well-known common cause of

pancreatitis. In general, the risk for pancreatitis occurs in patients with severe hypertriglyceridemia $>1000\text{mg/dl}$ ⁷⁸. However, the exact lower threshold of risk is not well defined. Although African-Americans have lower triglyceride concentrations compared to other US ethnic groups, there are no studies that would suggest that African-Americans have a higher population risk for pancreatitis at lower triglyceride concentrations. Therefore, in accordance with National Cholesterol Education Program ATP III guidelines, we propose using the current recommended triglyceride threshold of $\geq 500\text{mg/dl}$ for denoting increased risk for pancreatitis⁷⁸. In addition, any individuals with a personal or family history of medullary thyroid cancer or Multiple Endocrine Neoplasia syndrome type 2 will be excluded.

Weight $\geq 450\text{lbs}$

Individuals with weight $\geq 450\text{lbs}$ will be excluded because the maximum weight for the dual energy absorptiometry (DXA) scan is 450lbs.

Clinical and Laboratory Methods

Glucose Turnover

During the stable isotope tracer protocol, hepatic glucose production will be partitioned to evaluate rates of gluconeogenesis and glycogenolysis overnight and during a meal. Rates of glucose and glycerol turnover will be calculated as described below.

Rates of glucose appearance (Ra_{glucose}) will be calculated under near-steady-state conditions using the average enrichment of [6, 6-₂H₂]glucose into the systemic circulation using conventional isotope dilution calculations⁷⁷.

$$Ra_{\text{glucose}} = \frac{\text{Infusate enrichment}}{\text{Plasma enrichment}} \times \text{Rate of infusion of labeled glucose}$$

Under fasting and steady state conditions, rate of glucose appearance reflects hepatic glucose production.

Glucose production rate is the sum of the rates of gluconeogenesis and glycogenolysis [20]:

$$\text{Glucose production rate} = Ra_{\text{total}} - \text{rate of infusion of labeled glucose}$$

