Fractional gluconeogenesis will be determined using ²H₂O and the average enrichment of ²H enrichments of carbon 1,3,4,5,6 of glucose as previously described⁷⁹.

$$\text{Fractional gluconeogenesis} = \frac{\frac{(M+1)^2H(m/z169)}{6}}{^{2H}2O}$$

where (M+1)²H(m/z169) is the M+1 enrichment of ²H glucose measured using the mass-to-charge ratio (m/z) 170/169 fragment of glucose, 6 is the number of ²H labeling sites on the m/z 169 fragment of glucose, and ²H₂O is the enrichment in body water.

Absolute rates of gluconeogenesis and glycogenolysis will be calculated as follows:

$$\text{Rate of gluconeogenesis} = Ra_{\text{total}} \times \text{fractional gluconeogenesis}$$

$$\text{Rate of glycogenolysis} = \text{glucose production rate} - \text{rate of gluconeogenesis}$$

During meal ingestion, the Ra of dietary glucose into the plasma pool (Ra meal) will be estimated from the carbohydrate content in the liquid meal. We assumed that ~85% of orally ingested glucose enters the systemic circulation in the normal volunteers⁸⁰.

The rate of glycogenolysis during meal absorption (Glycogenolysis_{feed}) will be estimated as:

$$\text{Glycogenolysis}_{\text{feed}} = \text{Ra total} - (\text{Gluconeogenesis} + \text{Ra meal} + \text{infusion rate of labeled glucose})$$

Glycerol and Palmitate Turnover

Rates of appearance (Ra) will be calculated under near-steady-state conditions using the average enrichment of [²H₅]glycerol or [^{U-13}C₁₆] palmitate into the systemic circulation using conventional isotope dilution calculations⁷⁷.

$$\text{Ra} = \frac{\text{Infusate enrichment}}{\text{Plasma enrichment}} \times \text{Rate of infusion of labeled glycerol or palmitate}$$

Insulin Resistance

Hepatic insulin sensitivity we will be calculated using the hepatic insulin sensitivity index by measuring hepatic glucose production in relation to the fasting insulin concentration⁸¹. Since acute changes in insulin concentration decrease glycogenolysis but gluconeogenesis remains constant, glycogenolysis is the component of hepatic glucose production that is most sensitively regulated by insulin^{70,82}. Indices of hepatic sensitivity that include gluconeogenesis may underestimate the effect of hepatic insulin action and could blunt the assessment of insulin sensitivity. Therefore, we will also calculate a hepatic insulin sensitivity index using glycogenolysis and fasting insulin concentration⁸³.

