- i. Gastrointestinal upset: Nausea, vomiting and/ or diarrhea are common adverse reactions associated with liraglutide (Victoza®) occurring in 5-20% of patients (FDA labeling insert). Combination therapy of Victoza® and metformin slightly increases the incidence rate of nausea, vomiting and diarrhea to 9-24%⁶². In a 52-week randomized double blind controlled trial of liraglutide vs. placebo in 135 youth with type 2 diabetes treated with metformin, liraglutide was associated with a higher rate of serious adverse events although these were not associated with any specific finding or pattern. The most common adverse event noted in at least 5% of patients was: nausea (29%), vomiting (26%), diarrhea (23%) and abdominal pain (18%) and nasopharyngitis (17%)⁶³. The majority of all adverse events were mild in severity and resolved. There were no deaths reported. The symptoms were mild and resolved spontaneously within 1-4 days. The following actions will be taken to minimize the risk for gastrointestinal disturbance:
 - a. Liraglutide dosing will be gradually increased over 4-week period (Table 3).
 - b. Participants who experience mild to moderate gastrointestinal symptoms will contact the PI and the dose of liraglutide decreased incrementally for 1 week. If symptoms have resolved, the dose will be incrementally increased in 1-week intervals to achieve maximum dose of 1.8mg once daily.
 - c. Participants who experience severe and/or recurrent gastrointestinal symptoms will be withdrawn from the study.
- ii. Hypoglycemia: Victoza® lowers glucose by increasing glucose-dependent insulin secretion, lowering glucagon secretion and delaying gastric emptying. These actions result in lower fasting and postprandial glucose concentrations in the circulation; in adults, Victoza® can increase the risk of hypoglycemia at a rate of 0.24 episodes/ patient years. In youth treated with liraglutide and metformin, minor hypoglycemia occurred in 24% of patients and there were no cases of severe hypoglycemia⁶³. We will monitor the participants closely and the following precautions and actions will be taken to minimize the risk for hypoglycemia:
 - a. Blood glucose monitoring. Patients will monitor their blood glucose by either checking their fingerstick blood glucose levels at least twice daily (pre-breakfast and bedtime) or wearing an FDA-approved CGM device for the duration of the study.

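### Fed-state glycogenolysis subtracts a fixed 85% meal-glucose appearance in both arms; if liraglutide slows meal entry at week 12, the shortfall is counted as lower glycogenolysis on combination therapy only

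*Combined protocol and SAP*

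**What the plan says.** All references are to the combined protocol and SAP.

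- **Glucose Turnover (Clinical and Laboratory Methods)** announces that "hepatic glucose production will be partitioned to evaluate rates of gluconeogenesis and glycogenolysis overnight and during a meal". For the meal period, the appearance of dietary glucose (Ra meal) "will be estimated from the carbohydrate content in the liquid meal", with this constant: "We assumed that ~85% of orally ingested glucose enters the systemic circulation in the normal volunteers". No value specific to an arm, visit or participant is given. Fed glycogenolysis is then Ra total minus the sum of gluconeogenesis, Ra meal and the tracer infusion rate.
- **Visit 2, stable isotope administration.** Half of estimated daily energy is given as equal drink portions every 30 minutes over 5 hours, "using a continuous feeding protocol with a nutrient drink and [6,6²H₂]glucose intravenous infusion will be used to mimic the steady-state prandial state". Fed samples are taken at 270 to 300 minutes. The only glucose tracer described is intravenous. No oral meal tracer or measure of gastric emptying is described.
- **Liraglutide (Background)** lists among the drug's actions "reducing glucagon secretion and delaying gastric emptying". The hypoglycemia item under the liraglutide risks repeats this: "lowering glucagon secretion and delaying gastric emptying".
- **Visit 5.** "Participants will receive their last dose of study medication at supper in the evening of admission Day 1 during Visit 5". The fed test follows the next morning. The baseline test at Visit 2 comes after a 5 to 7 day drug-free run-in.
- **Analysis of Primary and Secondary Outcomes** contains no sensitivity analysis for the 85%.

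**The concern.** Fed glycogenolysis is a small remainder after a large assumed term is taken from a large measured one. If a drug changes the true size of the assumed term, measured Ra total moves and the subtracted constant does not. The difference falls into the remainder.

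Here the drug that the protocol says slows gastric emptying is given in one arm only, and it is present at week 12 but not at baseline. Slower meal entry on combination therapy would therefore look like stronger suppression of hepatic glycogen breakdown. The fed data as planned could not separate the two explanations. At stake is the fed-state mechanistic reading of the combination arm, not the primary comparison.

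**Working it through.** **1. The plan's own scale.** Sample Size Justification gives 80% power with 12 per group for a difference of 0.60 mg/kg LBM/min in glucose production (SD of change 0.50, two-sided alpha 0.05). Check: 0.60 / (0.50 × √(2/12)) = 2.94 on 22 degrees of freedom, which gives power of 80.2%, so the figure reproduces. It is used below only for a sense of scale. It belongs to glucose production; the documents give no SD for fed glycogenolysis.

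**2. Direction.** Write estimated glycogenolysis = Ra total − (gluconeogenesis + 0.85 × intake + tracer). True Ra total contains the true Ra meal, so

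error in fed glycogenolysis = true Ra meal − 0.85 × intake.

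Illustration with assumed values: gluconeogenesis 1.00, glycogenolysis 0.50, tracer 0.05, assumed Ra meal 8.05 (all mg/kg LBM/min).

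- True Ra meal 8.05: Ra total = 9.60; estimate = 9.60 − (1.00 + 8.05 + 0.05) = 0.50, which is correct.
- True Ra meal 7.25: Ra total = 8.80; estimate = 8.80 − 9.10 = −0.30, with the liver unchanged.

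Gluconeogenesis is Ra total × fraction. Meal glucose dilutes the fraction as it raises Ra total: 9.60 × (1.00/9.60) = 8.80 × (1.00/8.80) = 1.00. At steady state it is unaffected.

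**3. What cancels.** An error in the 85% that is the same at both visits drops out of the change. An error shared by both arms at week 12 drops out of the comparison. A liraglutide effect at week 12 does neither.

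**4. Size per percentage point.** From the documents: drink = 50% of daily energy, carbohydrate 50% of energy (matched to the previous day's meals), 300 minutes. Assumed: 4 kcal/g, energy needs 2200 to 3000 kcal/day, lean mass 50 to 65 kg.

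Intake rate = kcal × 0.5 × 0.5 / 4 × 1000 / 300 / LBM

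- 2200 kcal, 65 kg: 7.05 mg/kg LBM/min, or 0.07 per point.
- 2500 kcal, 55 kg: 9.47, or 0.095 per point; the assumed Ra meal is 0.85 × 9.47 = 8.05.
- 3000 kcal, 50 kg: 12.5, or 0.125 per point.

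**5. How far the feeding design limits the shortfall.** Assume first-order emptying with half-time h and portions at 0, 30, …, 270 minutes. Entry during 270 to 300 minutes, relative to the feeding rate, sums to 1 − 2^(−300/h). The documents give no value of h.

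| h (min) | Entry vs feeding rate | Shortfall, points of intake (× 85) | Error at 2500 kcal, 55 kg | Error over the step 4 range |
|---|---|---|---|---|
| 30 | 99.9% | 0.1 | −0.01 | about −0.01 |
| 60 | 96.9% | 2.7 | −0.25 | −0.19 to −0.33 |
| 90 | 90.1% | 8.4 | −0.80 | −0.59 to −1.05 |
| 120 | 82.3% | 15.0 | −1.42 | −1.06 to −1.88 |

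What biases the comparison is the slowing caused by liraglutide, not the week-12 shortfall itself. Slowing from 60 to 90 minutes gives (0.0992 − 0.0313) × 8.05 = 0.55 at the middle setting. Slowing that leaves h at 30 minutes or less gives almost nothing.

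**The case against.** The strongest reply has four parts.

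**The trial's hypothesis is untouched.** Aim 1 and the primary outcome concern gluconeogenesis, fasting and fed, and neither uses the 85%. This stands. A reader might infer that the bias favours the trial's main hypothesis; the formulas do not support that.

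**No listed outcome clearly depends on the constant.** Fed glycogenolysis is not named under Study Objectives. Glucose production is a secondary outcome, but the plan does not say that it is taken in the fed state, and its formula has no Ra meal term. This also stands: contamination of a listed secondary outcome cannot be asserted. What remains is that the methods commit to partitioning hepatic output during a meal, and the outcome list leaves fasting or fed unspecified. Any fed hepatic value must either remove meal glucose with the same constant or include it.

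**The feeding design already guards against this.** At a true steady state, slower emptying delays entry without lowering its rate. This stands in part. Step 5 shows a negligible error at short half-times. But the plan states only an intention to mimic steady state, does not address whether it holds on liraglutide, and includes no measurement that would show it.

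**The 0.60 is borrowed.** It is tempting to say that a shortfall of 4.8 to 8.5 points (0.60/12.5 to 0.60/7.05) would imitate the whole detectable difference. The arithmetic is right, but the comparison crosses two quantities. The 0.60 comes from pilot data on glucose production, and the pilot as described had no fed tracer period. It shows scale and nothing more.

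**Conclusion.** The point holds for fed glycogenolysis, and for fed hepatic glucose production if that is derived. A single constant from normal volunteers is applied to both arms, although the protocol's own account of liraglutide gives a reason why it could fail in one arm at one visit. Any such failure enters one-for-one, in the direction of lower glycogenolysis on combination therapy.

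The size cannot be fixed from the documents. It is about 0.07 to 0.125 mg/kg LBM/min per percentage point of shortfall, under the assumed energy needs and lean mass. The shortfall itself depends on an emptying rate that is not given: close to zero if emptying stays fast, several points if it is slow. The documents show that the bias is possible, not that it will occur. Fasting results do not use the constant. Fed gluconeogenesis does not either, provided that near-steady state holds.

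**What to change.** 1. State that gluconeogenesis is the only fed-state between-arm comparison to be interpreted as a liver effect.
2. State that the secondary outcome glucose production is the fasting value.
3. Report fed glycogenolysis, any fed glucose production and fed total Ra as descriptive. Total Ra belongs here too: it is measured, but it contains meal glucose, so delayed entry lowers it by the same mechanism.
4. Add a tipping-point analysis. Lower the week-12 appearance in the combination arm step by step below 85%, leave all other values at 85%, and report the shortfall at which the between-arm difference in fed glycogenolysis disappears. To a first approximation this is the observed difference divided by that arm's mean intake rate. For illustration, 0.60 / 9.47 = 6.3 points, an appearance of 78.7%.

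A reported tipping point is better than requiring the result to survive down to a fixed floor. No floor has a source in the documents, and a low one would be close to unpassable. At 70%, the correction of 15 points is 1.06 to 1.88 mg/kg LBM/min, whereas baseline glucose production minus gluconeogenesis in the pilot (Table 2) is only 2.93 − 1.78 = 1.15.

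The cost is a few lines of analysis and the loss of fed glycogenolysis as an inferential result. No new samples, visits or participants are needed.
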